## 1.0 OBJECTIVES

### 1.1. For phase I portion of study:

To determine the tolerability of the combination of decitabine and RUXOLITINIB (DI) in patients with leukemia.

### 1.2. For phase II portion of study:

Primary objective - To determine the efficacy of RUXOLITINIB in increasing and prolonging response induced by decitabine alone in patients with post myeloproliferative neoplasm AML (post MPN-AML) alternatively referred to as (myeloproliferative neoplasm- Blast phase; MPN-BP).(Compared to historical response rate with decitabine alone)

Secondary objective - To compare whether there is a difference in response rate patients with post-MPN AML with JAK2 mutations and patients without JAK2 mutations.

### 1.3. Endpoints:

1. Assessment of DLT and MTD
2. Proportion of patients achieving overall response (CR + CRI). We will also assess response by the MPN criteria (including ALR-C and ALR-P, see section 11.00)
3. Proportion of patients with post-MPN AML with JAK2 mutations and the proportion of patients without JAK2 mutations and any difference in response rate.

## 2.0 BACKGROUND AND RATIONALE

RUXOLITINIB phosphate is an inhibitor of the Janus kinase family of protein tyrosine kinases (JAKs) that has been recently approved for the treatment of patient with myelofibrosis and is undergoing further evaluation for the treatment of other myeloproliferative disorders under IND No. 77,456. Unless otherwise noted, RUXOLITINIB phosphate is referred to throughout this protocol as RUXOLITINIB. RUXOLITINIB Phosphate Tablets 5 and 25 mg (free base equivalent), as disclosed in IND No. 77,456, will be used in the proposed studies described in this IND. Additional details of the CMC characterization of RUXOLITINIB may be found in the Clinical Investigators Brochure (CIB).

We propose to investigate the combination of decitabine and RUXOLITINIB in patients with high-risk MDS/MPN and post-MPN AML. In the phase I portion of the trial, the aim is to determine the tolerability of the combination. In the phase II portion of the trial, the number and duration of responses in patients with post-MPN AML and high-risk MDS/MPN ( $\geq 20\%$  blasts) will be determined.

The Jak family of kinases comprises four proteins (Jak1, Jak2, Jak3, and Tyk2) that can associate with cytokine receptor subunits, phosphorylate them, and in doing so create docking sites on the receptors for binding of SH2-containing proteins. In general, Jaks consist of several domains (JH1-JH7), including a tyrosine kinase domain, and the functional significance of these domains has been characterized by mutational analysis. Jaks are able to associate with the cytokine receptors as well as with each other. Dimerization/oligomerization of cytokine receptor subunits as a result of ligand binding leads to juxtaposition of Jaks. This results in transphosphorylation and activation of their kinase activity and the phosphorylation of downstream signaling proteins such as Stats, Src-kinases, and adaptors such as Shc, Grb2, and Cbl.

Abnormalities of Jak function have been associated with a number of disorders. For example, chromosomal translocations resulting in TEL-JAK2 constructs lead to the constitutive activation of STAT5, IL-3-independent cellular proliferation, and leukemogenesis. The translocation t(9;12)(p24;p13) results in the fusion of the kinase catalytic region of JAK2 with the transcription factor TEL generating the constitutively active TEL-JAK2. Similarly, infection with oncogenic viruses such as human T-cell lymphotropic virus, type I, and Abelson murine leukemia viruses results in enhanced kinase activity of Jaks, possibly accounting for their leukemogenic potential.

The STAT transcription factors are coded by six known mammalian genes and include 10 different STAT proteins including different isomers of STATs 1, 3, 4, and 5. Like other transcription factors STATs have a well-defined structure including a DNA-binding domain, a conserved NH2-terminal domain, a COOH-terminal transactivation domain, and SH2 and SH3 domains. Their activation through tyrosine phosphorylation results in their dimerization and translocation into the nucleus where they activate specific genes.

Jak proteins activate a number of intracellular signaling proteins, among which STATs are the best defined. Binding of a cytokine to its receptor rapidly induces tyrosine phosphorylation of the cytoplasmic domains of the receptor by activated Jak kinases, thus providing a docking site for STAT proteins, which are then phosphorylated. This phosphorylation of STATs leads to their homo- or heterodimerization and translocation to the nucleus, followed by DNA binding and gene activation. The specificity for STAT phosphorylation is determined by the receptor docking sites and not the Jak kinases. Also, different STAT proteins have different DNA-binding affinities, resulting in activation of specific genes. STATs also interact with other transcription factors such as the p300/cyclic AMP-responsive element binding protein family of coactivators to activate genes. The transcriptional activity of STATs may also be regulated by the phosphorylation of their serine and threonine residues, although the implications of such regulation are not known.

STATs mediate diverse and sometimes opposite cellular events affecting growth, differentiation, and apoptosis. For example, STATs can mediate both growth arrest and cellular proliferation. Specifically, STAT1 mediates the growth-inhibitory effects of

IFN- $\gamma$ , through the induction of the CDKI p21waf1, whereas STAT5 mediates proliferative effects of IL-3 and GM-CSF. Similarly, phosphorylation of STAT3 can result both in IL-6- and IL-10-induced growth arrest, and in GM-CSF- and IL-3-induced proliferation. STATs also modulate cellular differentiation and apoptosis.

Reconstitution of STAT1 in STAT1-null U3A cells (which do not respond to TNF- $\alpha$ ) restores basal caspase expression and renders them sensitive to TNF-induced apoptosis. Conversely, STAT3 and STAT5 mediate the antiapoptotic effects of IL-6 and IL-2, respectively. STAT1 activates the caspase cascade through up-regulation of Fas and FasL expression in response to IFN- $\gamma$ . The exact mechanisms underlying these diverse effects are being elucidated.

Abnormalities of the JAK-STAT pathways have been described in a variety of leukemias and their inhibition can be a goal for leukemia therapy. Myelofibrosis (MF) is a clonal stem cell disorder with the potential to transform to acute leukemia (AML), referred to as myelofibrosis in blast phase (MF-BP). The outcome of patients with MF-BP is grave with a median survival of only 2.7 months. MF-BP is largely refractory to conventional chemotherapy and intensive induction therapy fails to have a significant impact with a median survival of 3.9 months.

Decitabine (5-aza-2'deoxyctidine) is a deoxycytidine analog originally synthesized in the 1960s. The compound is phosphorylated by deoxycytidine kinase prior to incorporation into DNA, and it is an S-phase-specific agent. Decitabine also inhibits DNA methyltransferases (DNMTs) by forming irreversible covalent bonds with DNMTs at cytosine sites targeted for methylation. At low doses, hypomethylation of DNA with subsequent gene reactivation and induction of cellular differentiation occur. At higher doses, cellular cytotoxicity predominates.

DNA hypermethylation of promoter-specific CpG islands is a well-known mechanism of epigenetic silencing, occurring frequently in cell cycle regulatory genes such as *p15INK4B* in a variety of hematologic malignancies, including MDS and AML. In MF, *p15INK4B* and *p16INK4A* hypermethylation has been reported to occur as the disease advances into accelerated and blast phases. Hypermethylation of the calcitonin gene (used as a marker of methylation at the 11p15 chromosome locus where several tumor-suppressor genes appear to cluster) has been reported in MF even in the chronic phase of the disease compared with other Philadelphia chromosome-negative chronic myeloproliferative diseases. In addition, the retinoic acid receptor  $\beta$  (*RAR $\beta$* ) gene has been found to be a target of epigenetic silencing in MF and has been proposed as a candidate tumor-suppressor gene in this disease. In clinical trials, decitabine has clinical activity in MDS at lower doses. Furthermore, a decrease in hypermethylation of the *p15INK4B* gene was observed in some patients with MDS following treatment with decitabine and correlated with clinical response. Significant evidence of clinical activity was also reported in a recent phase I study of decitabine at low doses in hematologic malignancies, but this study found no evidence of a

correlation of clinical responses with *p15INK4B* methylation, suggesting that the biologic effects of the drug may not be mediated solely through *p15INK4B* demethylation.

Our group has previously conducted a phase-II study to evaluate the activity of DNA methyltransferase inhibitor, 5-azacitidine, in patients with MF. Thirty-four patients (76% previously treated) received 5-azacitidine at 75 mg/m^2 subcutaneously daily for 7 days, every 4 weeks. Twelve (35%) patients had abnormal cytogenetics and 19 (70%) of 27 evaluable patients had JAK2(V617F) mutation. Responses occurred in 8 (24%) patients after a median of 5 months (range, 3-10). Partial response occurred in 1 (3%) patient (duration 22+ months) and clinical improvement in 7 (21%) patients (median duration 4 months; range, 2-8.5). Myelosuppression was the major adverse effect, with grade 3-4 neutropenia in 10 (29%) patients. Global DNA methylation assessed by the long interspersed nucleotide element (LINE) bisulfite/pyrosequencing assay decreased from 53% pretherapy to 44% on day 14 (P=0.0014) and returned to 50% at the end of the first 28-day cycle (P=0.016). 5-azacitidine is relatively well tolerated and results in induction of global hypomethylation in patients with MF, but results in limited clinical activity.

In another recently published study, 54 patients with Philadelphia-negative myeloproliferative neoplasm (MPN, including 21 essential thrombocythemia [ET], 21 polycythemia vera [PV], 7 primary myelofibrosis, and 5 unclassified MPN) who had progressed to AML (n = 26) or MDS (n = 28) were treated with azacitidine in a patient-named program. Overall response rate was 52% (24% complete response [CR], 11% partial response [PR], 8% marrow CR or CR with incomplete recovery of cytopenias, 9% hematologic improvement) and median response duration was 9 months. Prognostic factors were for overall response the underlying MPN (71% vs 33% responses in ET and PV, respectively; P = .016); prognostic factors for CR achievement were the underlying MPN (14% CR for PV vs 43% for ET; P = .040) and World Health Organization classification at transformation (36% vs 12% CR in MDS and AML, respectively, P = .038). Recurrence of chronic phase features of the initial MPN was observed in 39% of the responders. Median overall survival was 11 months. The authors concluded that azacitidine gives encouraging results in Ph-negative MPN having progressed to AML or MDS, but response duration is short, and consolidation treatments have to be evaluated.

We and others have also evaluated decitabine in the treatment of MF and have demonstrated significant activity. In a study from Mount Sinai School of Medicine, Four out of seven patients (57%) with MF-BP treated with decitabine reported subjective improvement in symptoms of fatigue/global weakness and left upper quadrant abdominal fullness/pain. All seven patients experienced an objective reduction in spleen size on physical examination with a mean 35% reduction of palpable splenomegaly (range 11–61%). Four out of seven patients (57%) had a decrease in RBC transfusion requirements and a single patient achieved transfusion independence after three cycles of therapy. The three patients who remain alive currently are in a morphologic complete response with incomplete platelet recovery (CRi) by IWG response criteria for AML

We have recently conducted a phase II study of RUXOLITINIB in patients with relapsed/refractory leukemias for which no standard therapies were anticipated to result in a durable remission. Patients with acceptable performance status (0-2) with adequate organ function and no active infection received RUXOLITINIB 25mg orally twice a day for 4 weeks (1 cycle). Response was assessed after every 2 cycles of treatment. Responding patients or patients with stable disease were allowed to continue until progression. Dose escalation to 50 mg twice daily was permitted in patients demonstrating a benefit. 38 patients with median age 69 (range 45-88) with relapsed and refractory leukemias were treated. The median number of prior therapies was 2 (range 1-6). 12 patients had JAK2V617F mutation. Patients who completed 2 cycles of INCB with clinical improvement were defined as having stable disease (SD). Patients received a median of 2 cycles of therapy (range 1-22). Three patients with AML developing after prior MF (MF-BP) showed remarkable response with 2 achieving complete remission (CR) and one remission with insufficient platelet count (CRI). 12 patients had SD. Responding patients have had a significant reduction in their spleen size. Overall INCB was tolerated very well.

**Rationale:**

There is no standard medical treatment for MF-BP or other post-MPN-AML. We believe that the combination of ruxolitinib and decitabine is a candidate approach to the treatment of MF-BP that is worthy of exploration based on the current understanding of the biology of disease. The molecular pathogenesis of MPN and progression to blast phase is almost certainly due to a complex combination of gene mutations (JAK2V617F, MPL) and epigenetic alterations (IDH1/2, IKZF1, EZH2, TET2) that culminate in the emergence of leukemic clones. Recent evidence indicates that the JAK2V617F protein can localize in the nucleus and influence global DNA methylation patterns which may lead to genomic instability and disease progression (40, 41). The inhibition of JAK-STAT mediated cell proliferation and survival in conjunction with the reversal of DNA hypermethylation of tumor suppressor genes would be predicted to have at least an additive if not synergistic effect in inducing apoptosis of cells belonging to the malignant myeloid clone. Correlative studies conducted within a trial of combination JAK2 inhibitor and DMNT1 inhibitor in patients with MPN-BP would explore the effect on methylation status of various gene promoters as well as the influence on gene expression of chromatin related proteins and ultimately leukemic cell survival. The sequential administration of a JAK2 inhibitor followed by a DNMT inhibitor would also potentially serve to overcome the JAK2-independent effects of epigenetic lesions that lead to MPN-BP.

**3.0 STUDY DESIGN****3.1 Design**

In this non-randomized Phase I/II investigator-initiated, single center trial, cohorts of patients will be treated with increasing doses of ruxolitinib in combination with a decitabine at a dose of 20mg/m^2 daily intravenously over 5 days. We will use an initial dose of ruxolitinib of 10 mg orally twice daily. Patients will receive ruxolitinib for the first 28 days in addition to decitabine on days 1-5 of each cycle. Cycles will be repeated every 4-6 weeks depending on tolerance and the recovery of the counts. Patients who become eligible for allogenic stem cell transplant may leave the study at any time after the first cycle.

After the first cycle of therapy, modifications to the dose of Ruxolitinib felt to be in the best interest of the patient are allowed after discussion with the Principal Investigator of the study and with the documentation of the discussion in the patient's medical records.

For the purposes of assessing safety, DLTs will be defined as those adverse events occurring in the first cycle (i.e. 28 days) of therapy that are not clearly related to disease, intercurrent illness or concurrent medication. These events will be defined based on the NCI CTCAE version 4 as follows:

- Any Grade 3 or higher non-hematologic toxicity (with the exceptions of Grade 3 or higher nausea, vomiting, or diarrhea, which will be considered DLTs only after optimal prophylactic measures have been prescribed; Grade 3 elevations of AST/ALT must be sustained for more than 4 days or reach Grade 4 to be considered a DLT. Grade 3 elevations in bilirubin must occur in the setting of a direct bilirubin >1 to be considered a DLT. Fatigue must be Grade 4 to be considered a DLT)
- Any Grade 4 hematologic toxicity lasting at least 42 days from the first day of the last cycle of therapy with a bone marrow cellularity of ≤5% and no evidence of leukemia. No dose modification will occur until any potential DLTs is fully assessed

MTD is defined as the highest dose studied for which the incidence of DLT is less than or equal to 17% (1 out of 6).

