**Table 1 – RUXOLITINIB dose**

Dose level	RUXOLITINIB (mg PO) (x 28 days)	No of evaluable patients
0	10 BID	3
1	15 BID	3
2	25 BID	3
3	50 BID	3

We will utilize the above design format to determine the tolerable dose of RUXOLITINIB to be used in combination with decitabine, with 25 mg PO BID as the target dose. The enrollment of participants will be staggered; all the participants in each cohort will finish the first cycle of therapy followed by 7 days of observation (i.e. day 35 of therapy) before proceeding to the next cohort. Subsequence cycles will begin on the first day of decitabine therapy and, in the absence of toxicity, RUXOLITINIB administration will not be interrupted. Patients who come off the study during the first cycle for reasons other than development of dose limiting toxicity (e.g. disease progression) will be replaced in order to ensure adequate chance for the assessment of DLT.

If grade 3-4 non-hematological RUXOLITINIB-related toxicities are observed in ≥ 2/6 patients, this dose level would exceed the MTD.

If grade 3-4 RUXOLITINIB-related toxicities are observed in 0-1/6 patients, the study will continue at the RUXOLITINIB dose of 15, 25, and 50 mg P.O. BID x 28 days plus chemotherapy, as outlined above. We will examine the dose of 50 mg BID to assess its tolerability and if well tolerated, this will be the dose to move to phase II. However, the target dose for phase II is 25 mg po BID x 28 days.

Cycles will be repeated approximately every 4 to 6 weeks, depending on the recovery of the blood counts and will continue until clinically significant progression, withdrawal of consent or unacceptable toxicity for a maximum of 24 cycles (see section 13.0).

Toxicities to be monitored include any grade 3 or 4 non-hematological toxicity felt to be related to RUXOLITINIB and prolonged cytopenias (lasting for more than 42 days after the initiation of the treatment) felt to be related to the treatment and not the underlying disease. Patients with prolonged cytopenias should have a bone marrow exam around day 42 to establish whether this is due to the treatment or whether there is persistent disease. In the case of the former, treatment should be discontinued.

Prior to advancing/changing dose levels, a cohort summary must be completed and submitted to the IND Medical Monitor for review.

Each cohort will have up to 6 patients enrolled.

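### Phase I: a cycle 1 death recorded only under a hematologic term cannot meet the DLT definition and, read literally, is replaced rather than counted in the 3+3 rules (a narrow gap)

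*Combined protocol and SAP*

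**What the plan says.** Sections 3.1 and 8.3 define a DLT by two limbs, both confined to the first cycle of 28 days and to events "that are not clearly related to disease, intercurrent illness or concurrent medication".

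- **Non-hematologic limb:** Grade 3 or higher, with listed exceptions. Fatal events are therefore included.
- **Hematologic limb:** "Any Grade 4 hematologic toxicity lasting at least 42 days from the first day of the last cycle of therapy", in a marrow at or below 5% cellularity and free of leukemia. Neither section says how a death is classed.

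Section 8.1, under Table 1, sets the replacement rule: "Patients who come off the study during the first cycle for reasons other than development of dose limiting toxicity" (progression is the example given) "will be replaced in order to ensure adequate chance for the assessment of DLT". The same text has two toxicity sentences. One reads "If grade 3-4 non-hematological RUXOLITINIB-related toxicities are observed in ≥ 2/6 patients, this dose level would exceed the MTD". The other reads "If grade 3-4 RUXOLITINIB-related toxicities are observed in 0-1/6 patients, the study will continue", with no restriction to non-hematologic events. It also says "Each cohort will have up to 6 patients enrolled", and that before any change of dose level "a cohort summary must be completed and submitted to the IND Medical Monitor for review".

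Further on in 8.1, the rule for opening phase II refers to ruxolitinib-attributed first-cycle toxicity and names no grade. Section 6.0 allows up to 6 replacements in phase I. Section 8.2 counts evaluable patients without defining the term, and section 12.0 lists death among the reasons for leaving the study.

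**The concern.** Two deaths that are clinically alike can be treated differently according to the recorded term. A neutropenic patient whose death is recorded as sepsis is a DLT. If the only recorded term is a cytopenia, or febrile neutropenia classed as hematologic, no DLT limb is met. The patient has then left cycle 1 for something other than a DLT, which is the literal trigger for replacement.

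The MTD rests on 3 to 6 patients per level, so one uncounted event changes the decision. Myelosuppression is expected from both drugs (section 10.0). Phase II monitoring in section 13.0 uses hematologic toxicity of grade 4 or above without a duration condition, so a fatal hematologic event would count there.

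**Working it through.** **The plan's own figure.** The MTD threshold is 1 of 6: 1/6 = 16.7%, which rounds to the stated 17%.

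**Timing.** A death in cycle 1 occurs by day 28. Cytopenia counted from day 1 of that cycle has then lasted at most 28 days, and 28 < 42. The duration condition cannot be met, whatever the marrow shows.

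**Counting, with no assumed rate.** Take one such death among the first 3 patients and no other DLT.

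- If counted: 1 of 3, so up to 3 more patients are treated at the same level (8.2 and section 13).
- If replaced: 3 evaluable patients among 4 enrolled, 0 DLTs, so 8.2 and section 13 escalate. Four enrolled is within the 6 per cohort in 8.1, and one replacement is within the 6 in section 6.0.

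**Illustration at assumed rates.** The documents give no rate for such deaths. Let q be that rate. The 3+3 probability of clearing a level at per-patient DLT rate x is f(x) = (1−x)³ + 3x(1−x)⁵.

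*(a) No other DLTs.* If deaths count, the level clears with probability f(q). As written, it clears if 3 of at most 6 enrolled patients survive cycle 1.

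| q | Deaths count, f(q) | As written |
|---|---|---|
| 5% | 0.973 | 0.9999 |
| 10% | 0.906 | 0.9987 |
| 20% | 0.709 | 0.9830 |

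*(b) Other DLTs at an assumed, independent 10%.* If deaths count, x = 1 − 0.9(1−q), which is 0.145, 0.190 and 0.280. As written, a patient is replaced only if the death comes without another DLT (probability 0.9q). The DLT rate among evaluable patients is then 0.1/(1−0.9q), which is 0.105, 0.110 and 0.122. The capped columns follow each enrolled patient in turn (DLT 0.1, replaced 0.9q, otherwise neither) and stop at 6 enrolled.

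| q | Deaths count | As written, no cap | As written, at most 6 enrolled | Unresolved at 6 |
|---|---|---|---|---|
| 5% | 0.824 | 0.898 | 0.855 | 0.049 |
| 10% | 0.730 | 0.889 | 0.809 | 0.093 |
| 20% | 0.536 | 0.868 | 0.727 | 0.171 |

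With the cap, the as-written rule clears a level more often by 0.855 − 0.824 = 0.031, 0.809 − 0.730 = 0.079 and 0.727 − 0.536 = 0.191.

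If the two rates are added instead of treated as independent, the counted figures are 0.814, 0.709 and 0.494, against 0.897, 0.887 and 0.862 with replacement and no cap. The direction is the same.

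**The case against.** **The deaths most to be expected already count.** Section 10.0 anticipates infection from myelosuppression, and a fatal infection, sepsis or hemorrhage meets the non-hematologic limb. The clearest candidate for the gap is febrile neutropenia. Only Table 2 places it under a hematologic heading, and that table governs dose modification; the DLT text does not class it. CTCAE version 4 and Appendix E are not among the documents, so how often a death would carry a hematologic term alone cannot be judged. All of this stands and makes the gap narrow.

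**Section 8.1 may count the event.** The continuation sentence is not limited to non-hematologic toxicity, so a ruxolitinib-related Grade 4 cytopenia before death could count there. The phase II opening rule names no grade and could count it too. A reader might infer that even two such deaths would lead to escalation, on 0 of 3 after 5 enrolled. Under 8.2 and section 13 alone that arithmetic is right. However, two attributed Grade 4 cytopenias could fail the 0–1 of 6 condition in 8.1, while the neighbouring MTD-exceeded sentence would ignore them. The documents conflict; they do not clearly escalate.

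**Replacement is meant for something else.** Its stated purpose is an adequate chance to assess DLT, and its example is progression. A reader might infer that the plan exempts treatment-related deaths. No text says so, and a careful investigator could well count one. The medical monitor's cohort review and SAE reporting would make the death visible, and dose changes wait until potential DLTs are assessed. These are real safeguards, but none of them adds the death to the 3+3 count.

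**A death clause could sweep in disease deaths.** Section 2.0 gives a median survival of 2.7 months in blast-phase myelofibrosis. Assuming exponential survival, 28 days (about 0.92 months) gives 1 − 2^(−0.92/2.7) ≈ 21% dying in that time. This objection fails as a reason against the change: the same exclusion of clearly unrelated causes already governs every fatal non-hematologic event.

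**Conclusion.** The point holds in a narrow form and is minor. In 3.1 and 8.3, whether a cycle 1 death with no clear excluded cause is a DLT depends on the recorded term. If the term is hematologic only, it cannot be one. Read literally, the patient is then replaced, and the rules in 8.2 and section 13 do not count the death.

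The certain consequence under those rules is that one such death in the first 3 patients can turn expansion at 1 of 3 into escalation on 0 of 3 after 4 enrolled. This rests on a literal reading of the replacement sentence and on a death with no non-hematologic term. The probabilities in the tables are illustrations at assumed rates, not estimates for this trial. The decision to leave transient febrile neutropenia out of the DLT definition is not questioned.

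**What to change.** 1. In 3.1 and 8.3 add: *Deaths in cycle 1* "that are not clearly related to disease, intercurrent illness or concurrent medication" *are DLTs whatever term is recorded, without the 42-day and marrow conditions.*
2. In 8.1, after the replacement sentence, add: *Patients who die in this way are evaluable for DLT and are not replaced.*

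Attribution stays with the investigator under the existing standard. Two other edits may suggest themselves but would not do the job. Extending the hematologic limb to Grade 4 or higher captures no cycle 1 death while the 42-day condition stays. Changing grade 3–4 to grade 3 or higher in the two toxicity sentences of 8.1 leaves their conflict over hematologic events unresolved.

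The cost is protocol wording only, with no added visits or tests. The downside is a possibly higher DLT count and so a lower MTD.
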